PPI is generally viewed as a measure of automatic, preattentional inhibition (17). It is regulated by circuits connecting portions of the prefrontal and mesial temporal cortex, with subcortical systems extending from the basal ganglia to the pons (101). Drugs acting at prominent nodes in this circuitry have potent effects on PPI (108). For example, PPI is **increased** in HS by the NMDA antagonists ketamine (1,15), amantadine (105) and MEM (107). We first reported the PPI-enhancing effects of MEM (20 mg po) in HS (107); these findings were extended as seen in Fig. 2. MEM (20 mg) significantly increased PPI in SZ patients (Fig. 2A), across 10-120 ms prepulse intervals; comparable effects were detected in HS at 60 ms intervals, which is a critical “sensitive” temporal window for therapeutic drug effects (103). Interestingly, these potent MEM effects in SZ patients were evident despite the fact that, as a group, these patients were not deficient in PPI, consistent with the fact that 90% were taking PPI-normalizing second generation antipsychotics (SGAPs) (48,103,123).

[figure not shown]
MEM effects on PPI are moderated by age and baseline PPI level, but not by AP load, anticholinergic load or demographic or clinical variables (5,99). These findings support the strong prediction that PPI will be a potent signal of MEM “bioactivity” in this application – a quantifiable measure of MEM’s activity within the brain, and specifically within PPI-regulatory circuitry that includes elements relevant to the pathophysiology of AD - and might conceivably serve as a “biomarker” predicting therapeutic response to MEM among AD patients.

2. **MMN** is an auditory event-related potential (ERP) component 50-150 ms after a deviant, “oddball” stimulus is presented within a sequence of repetitive standard sounds (Fig. 5: shown, from mild-to-moderate AD patients, n=20 ([name])); it reflects the properties of automatic, memory-based comparison processes (cf. 74). It is rapidly assessed, and while it is highly stable in normal and impaired patient populations across the lifespan (63), studies of this form of MMN in AD patients have reported inconsistent results, with many studies reporting no differences vs. age-matched HS (21,76-7). MMN is largely automatic and preattentional, yet it is strongly associated with neurocognition and psychosocial function, even in HS (64).

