deficient in SZ (49), even at first episode (96); in contrast, the literature on ASSR in AD patients is inconsistent, reflecting a lack of standardized paradigms for eliciting ASSR across these studies (eg. 75,116,118). Gamma oscillations are enhanced by MEM in rodent models (29,67) and by ketamine in both rodents and HS (31,33,50). Our recent studies (Fig. 2) detected deficits in ASSR gamma evoked power and phase locking in SZ patients, that were significantly corrected by MEM. However, MEM-enhanced gamma power and phase locking was also detected in HS (Fig. 2C-D) (65). These findings support the strong prediction that ASSR metrics will be a potent signal of MEM-sensitivity in this application. The PI and Co-PI ([name]) have published extensively on the characterization of the ASSR and its deficits in patients vs. HS (39,59-62).

[figure not shown]
[figure not shown]

Fig. 6. ASSR in AD patients (n=20): (γ power, phase locking (PL)): 40 Hz clicks/tones (left) drive γ power and PL in the EEG; this may reflect capacity of the auditory system to generate oscillations in synchrony with the stimuli. At right, γ PL time-frequency plot: x-axis: time in ms; y-axis: frequency. Color = PL factors.

The extant literature does not make a strong prediction regarding levels of baseline EAIP performance in AD patients. It is thus important to emphasize that the prediction of MEM-enhancement of these EAIPs in AD patients is independent of the presence of any AD-related EAIP deficiency. For example, MEM enhances PPI, MMN and ASSR in HS (65,99,101) (who by definition do not have EAIP deficits), and MEM enhances PPI in SZ patients whose PPI has been “normalized” by SGAPs (103,123). Furthermore, MEM-enhanced EAIP was detected in patients despite the presence of a variety of psychotropic medications (including SGAPs) that potentially will also be used by the AD patients in this application. *Thus, the ability to detect the proposed biomarker for MEM-sensitivity in this application should not be impeded by the presence (or absence) of abnormalities in baseline EAIP levels or the use of psychotropic medications in the AD patient group.*

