Aim 1 tests EAIP MEM sensitivity in patients with mild-to-moderate severity AD, in a double blind, within-subject cross-over design of MEM (20 mg po) vs. PBO. The primary result of Aim 1 is a biomarker characterization of "EAIP MEM-sensitivity" for each subject. Patients are also screened for baseline outcome and neurocognitive measures. In Aim 2, all patients titrate to 10 mg MEM bid, and outcome measures are collected at 8, 16 and 24 weeks. Analytic strategies are then used to test the hypothesis (H2) that greater EAIP MEM sensitivity predicts greater clinical MEM sensitivity.

Detailed Methods:

Stimulus parameters: The rationale for startle and ERP stimuli reflects both **empirical** and **theoretical** considerations, as discussed in our published reports (99,103). Empirically, these stimuli and session designs detect consistent MEM effects on PPI, MMN and ASSR (Fig. 2), and thus afford us the strongest predictions in terms of MEM effects in this application. There are also pragmatic considerations specific to each measure; for example, weaker pulse intensities generate smaller startle responses, and with the habituation resulting from repeated testing (2 test days), this results in an unacceptable number of startle "non-responders". Space does not allow a full description of the many such decision points with each measure, which are supported by a rich literature and the PI's and Co-PI's > 30 years of published experience.

Startle and PPI are assessed as in (99), with 42 trials, of 6 types: a 118 dB(A) 40 ms noise (pulse), and pulse preceded 10, 20, 30, 60, or 120 ms by a prepulse 16 dB over a 70 dB(A) background. Primary measure: **MEM effect (MEM minus PBO) on mean %PPI with 60 ms prepulse intervals**. Total time: 30 min, with clean-up.

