Aim 1: Repeated measure (Rm)-ANOVAs will determine whether PPI, MMN and ASSR significantly differ after MEM vs. PBO (Hypothesis 1). Primary variables for each EAIP, as well as exploratory "secondary" measures, are identified above. Based on a recruited sample of 88 total participants, we will have 80% power to detect effect sizes of $d = 0.35$ (small) using a Bonferroni corrected $\alpha = .05/3$ (2-tail). Heterogeneity of response will be characterized using variance components expressed as intraclass correlation coefficients (ICCs).

Aim 2: Linear mixed-effects models regressing change in ADAS-cog outcome scores (at 8, 16, and 24 weeks vs. baseline) onto a fixed effect of group defined by MEM sensitivity will test the hypothesis that patients exhibiting a larger "MEM effect" on EAIP measures will exhibit a larger positive clinical response to MEM. Groups will be defined by a median split of "MEM effect" (MEM minus PBO) on EAIP. Power was estimated using methods described by Hedeker et al. (25) solving for sample size with $\alpha = .05$ (2-tail), test-retest correlations of .50, and 5% attrition at each time point. A sample of 88 total participants provides us with 80% power to detect a medium effect of $d = 0.50$. The primary outcome will be chosen based on effect sizes obtained as part of Aim 1. In exploratory analyses, we will also examine group by time interactions using orthogonal polynomial contrasts. We will also predict change in clinical outcomes as a function of all four candidate biomarkers in order to create an optimal prediction equation. We will perform ROC curve analyses using EAIP MEM sensitivity values as continuous variables and predict clinical improvement after MEM as a discrete outcome (responders vs. non-responders) in order to determine the clinical utility of this approach defined in terms of sensitivity and specificity. Secondary analyses will also be conducted with biomarker groups defined as "MEM-sensitive vs. -insensitive" via specific thresholds for EAIP MEM sensitivity.

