Analyses to test H2 will also utilize primary, secondary and exploratory metrics of **MEM's clinical effects**:

1. **primary** outcome measure: ADAS-cog, change from baseline;
2. **secondary** outcome measures: NPI-Q and Geriatric Depression Scale (change from baseline);
3. **exploratory** outcome measures: ADAS-cog factor-derived subscales (change from baseline) (eg. 81).

Factors that moderate the relationship of the primary biomarkers (EAIP MEM sensitivity) and clinical outcome will also be explored, including: 1. Genetic markers (GRIN, APOE, described above); and 2. Patient characteristics (eg. age; past AD medications; baseline (T0) neuropsychological and outcome measures).

Lastly, we will probe the specific anatomical basis of MEM effects on MMN and ASSR using **source locali-**

zation techniques (109,124); conceivably, these analyses will provide information more generally relevant to the anatomical basis for MEM's therapeutic actions, i.e. the "mediators of the therapeutic intervention", as described in this PAR. A simple model for such mediation might be: "MEM action on 'structure X' → EAIP change → enhanced therapeutic sensitivity," but more complex, circuit-based models will also be explored.

For simplicity, this application associates greater "EAIP MEM sensitivity" with an EAIP-enhancing response to MEM challenge (eg. EAIP (MEM minus PBO) > median value); this approach is parsimonious because arithmetically larger EAIP values are generally associated with positive neurocognitive and functional change (21,56,58,64,111). However, one might rationally argue that *any significant change in response to MEM challenge reflects "MEM sensitivity", and thus directionality of the MEM response should not be assumed*. Thus, while we represent arithmetically larger MEM responses as "MEM-sensitive" in this application, Aim 2 analyses (linear mixed-effects model) make no assumptions of directionality; exploratory categorical analyses will also define "MEM sensitivity" based on the absolute change in EAIP amplitude (i.e., positive or negative).

Important questions related to experimental design and analysis:

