8. Assist the NIA by commenting on any problems with study conduct, enrollment, sample size, and/or data collection.
9. Considering the overall picture, including need to pursue both primary and appropriate secondary analysis, and making these recommendations during the data analysis phase of the project;
10. Reviewing final results, via DSMB report by PI within 90 days of completion of final study subject.

Inclusion of Women and Minorities

Inclusion of women: Women will be included in this study. One key dependent measure (PPI) exhibits clear sexual dimorphism; previous studies of memantine effects detected **no interactions of sex with drug or diagnosis** for any of the proposed measures of early auditory information processing (PPI, MMN or ASSR). Importantly, it is possible that a significant effect of memantine on auditory processing measures, or an interaction between memantine sensitivity and potential moderating factors (e.g. age, baseline performance, single nucleotide polymorphisms) will be evident in only one or the other sex, or that relationships among specific measures might be sex-specific. Thus, there is a strong rationale for assessing the predicted drug effects in both men and women, to test specific predictions of drug-behavior relationships.

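### The H2 test uses an unadjusted MEM-minus-placebo score and never examines placebo-day EAIP, so, for PPI at least, it cannot separate a response to the challenge from resting level

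*Combined protocol and SAP*

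**What the plan says.** Under the statistical tests for each hypothesis, Aim 2 regresses ADAS-cog change at weeks 8, 16 and 24 "onto a fixed effect of group defined by MEM sensitivity". The grouping rule is "Groups will be defined by a median split of" the MEM-minus-placebo difference. For PPI the score is the "MEM effect (MEM minus PBO) on mean %PPI with 60 ms prepulse intervals". The continuous version described under Multiple analytic strategies uses the same sensitivity score. The section on sex as a biological variable adds sex as a factor, and no other adjustment is named.

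On resting level, the PPI paragraph of the EAIP measures section states that "MEM effects on PPI are moderated by age and baseline PPI level". No equivalent statement is made for MMN, gamma power or phase locking. The moderators listed under Secondary / Exploratory Analyses include "baseline (T0) neuropsychological and outcome measures". That list is open-ended but does not name placebo-day EAIP. The section on inclusion of women mentions "potential moderating factors (e.g. age, baseline performance, single nucleotide polymorphisms", only as possibilities and with no analysis attached.

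The plan also links EAIP level to clinical status. The MMN paragraph ties MMN to neurocognition and psychosocial function, and the secondary-analysis section treats larger EAIP values as generally favourable. The section on why there is no control group confirms that every patient receives MEM.

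**The concern.** The trial's claim is that a drug challenge identifies patients who will respond. A difference score can carry two signals: how a patient reacts to the pill, and where the patient stood without it. Where the reaction depends on the resting level, as the plan reports for PPI, splitting on the difference also splits on resting level. If resting level predicts ADAS-cog change, the two halves will differ clinically for a reason unrelated to the challenge. With no untreated arm, nothing else in the design separates prognosis from drug response.

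Both kinds of error are possible. A positive H2 might be available from one placebo-day recording, with no challenge dose. Or a real challenge effect might be hidden because the halves start from different resting levels. The planned model cannot tell these apart, although the placebo-day value is collected from every patient who completes testing.

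**Working it through.** **The plan's own figure.** Inputs from the Aim 2 text: 88 patients (44 per half), d = 0.50, two-sided alpha 0.05, correlation 0.50, 5% attrition per time point. Take three post-baseline visits with retention 1, 0.95 and 0.9025. The variance of the averaged contrast is (3.1607 + 3.1586)/9 = 0.702, so SD = 0.838. Power = Φ(0.5/(0.838 × √(2/44)) − 1.96) = Φ(0.839) = 0.80. The stated power reproduces; the sample size is not in question.

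**Model for the bias.** Let T be stable resting EAIP, with day-to-day noise e1 and e2:
- placebo day: P = T + e2, with total variance 1, Var(T) = r and Var(e) = 1 − r
- MEM day: M = T + c − sT + e1, where s is the fall in MEM effect per unit of resting EAIP
- score: D = M − P = c − sT + e1 − e2
- correlation of T with ADAS-cog improvement: b

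Then corr(D, T) = −s√r / √(s²r + 2(1 − r)), and the median-split difference is d = 2√(2/π) × b × corr(D, T) = 1.596 × b × corr(D, T).

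The documents give none of r, s or b. The assumed ranges are r = 0.5 to 0.8, s = 0.25 to 0.5 and b = 0.2 to 0.3.

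| s | r | corr(D, T) | absolute d, b = 0.2 | absolute d, b = 0.3 |
|---|---|---|---|---|
| 0 | any | 0 | 0 | 0 |
| 0.25 | 0.5 | −0.174 | 0.056 | 0.083 |
| 0.25 | 0.7 | −0.261 | 0.083 | 0.125 |
| 0.25 | 0.8 | −0.333 | 0.106 | 0.160 |
| 0.5 | 0.5 | −0.333 | 0.106 | 0.160 |
| 0.5 | 0.7 | −0.475 | 0.152 | 0.227 |
| 0.5 | 0.8 | −0.577 | 0.184 | 0.276 |

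Simulation of the same model (n = 88, 20,000 runs per setting, one averaged outcome per patient) gives 0.053 to 0.275, reported here as about 0.05 to 0.27. With no challenge-specific link to outcome, the unadjusted test rejects in 5.5% to 25% of trials when s is 0.25 or 0.5, and in about 5% when s = 0.

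These d values are per SD of a patient's average change. Per single-visit SD they are multiplied by 0.838, giving about 0.04 to 0.23.

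**Direction.** With b and s both positive, the higher-MEM-effect half has lower resting EAIP and does worse, which works against H2. If low EAIP goes with better change, the bias favours H2. The plan does not state the direction of the PPI moderation, so s could also be negative.

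**What adjustment does.** In the same simulation with s = 0, adding P as a covariate makes the MEM-effect term reject in about 7% to 14% of trials (median split) and 9% to 21% (continuous). Because P is a noisy reading of T, the MEM-day value acts as a second measurement of T. With s at 0.25 to 0.5 the adjusted coefficient is biased by about +0.06 to +0.16 where the unadjusted one is biased by −0.05 to −0.27. The two errors have opposite signs when the MEM effect falls with resting level, so agreement between them is informative and the adjusted result alone is not.

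**The case against.** The strongest objection is that a difference score is not biased merely because the placebo value is subtracted. That is correct. A reader might take corr(D, P) = −√((1 − r)/2), which is −0.50, −0.39 and −0.32 for r = 0.5, 0.7 and 0.8, multiply by b and 1.596, and infer a spurious d of 0.10 to 0.24 for all four measures. If every patient has the same MEM response, that coupling runs only through the placebo day's random fluctuation. Stable resting level cancels from D. Unless a single day's fluctuation itself predicts 24-week change, the bias is zero.

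A reader might also infer that the plan reports dependence on baseline for EAIP in general. It does so for PPI only, and not in AD patients.

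Nor does the ASSR section contradict the PPI section. Its statement that detection "should not be impeded by the presence (or absence) of abnormalities in baseline EAIP levels" means that no AD-related deficit is needed to see the biomarker. It does not say that response size is independent of resting level, and it needs no correction.

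The open moderator list and the plan's concession that EAIP response may be a general rather than MEM-specific predictor give partial cover. Neither commits to examining placebo-day EAIP.

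What remains is the conditional problem: dependence of response on resting level, reported for PPI, combined with prognostic value of resting level, which the plan's own links make plausible.

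**Conclusion.** The gap is real and should be closed, but it is conditional. If true MEM response depends on stable resting EAIP and resting EAIP is prognostic, H2 is biased by about 0.05 to 0.27 in absolute d, or roughly 10% to 54% of the planned 0.50 (9% to 46% on the single-visit scale). If response does not depend on resting level, the bias is about zero. The range rests entirely on assumed r, s and b and is not a ceiling: r = 0.9, s = 0.5 and b = 0.3 gives 1.596 × 0.3 × 0.728 = 0.35. The case is best supported for PPI. For the other three measures it is a possibility worth checking.

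It would be wrong to conclude that H2 will be falsely positive, or that covariate adjustment settles the matter. The direction is open, and the adjusted model has an error of its own.

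**What to change.** Keep the powered unadjusted test as primary. In the Aim 2 statistical text, prespecify for PPI and each other primary EAIP measure two supporting models of ADAS-cog change, reported beside the unadjusted result:
- (a) placebo-day EAIP alone
- (b) the MEM effect plus placebo-day EAIP

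State the reading rule in advance:
- Make a challenge-specific claim only if the unadjusted test is positive and the adjusted coefficient has the same sign and supports it.
- Never use the adjusted result alone to recover a negative H2.
- Call the finding a resting-EAIP predictor only if model (a) shows one, not merely because the adjusted term is non-significant.

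The cost is SAP wording and two extra models per measure on data already collected; power of the primary test is unchanged. The adjusted estimate is less precise. With s = 0 its standard error is larger by a factor 1/√(1 − (2/π) × corr(D, P)²), which is 1.09, 1.05 and 1.03 for r = 0.5, 0.7 and 0.8. Under strong dependence it is worse: at s = 0.5 and r = 0.8, corr(D, P)² = 0.36/0.60 = 0.60 and the factor is 1.27. Making adjustment primary would lower power at N = 88 to about 0.73, 0.76 or 0.78 for r = 0.5, 0.7 or 0.85, even with s = 0.

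Two limitations should be written into the plan. One placebo-day reading is noisy, so the adjusted MEM-effect coefficient can absorb stable resting EAIP. And if the MEM effect rises with resting level, the unadjusted and adjusted errors share a sign, so model (a) is then the main warning.

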How will we address “incomplete” (MEM dose < 10 bid) or discontinued subjects? It is possible that the proposed biomarkers (eg. “MEM-insensitive” EAIP) will predict the likelihood to *discontinue* MEM treatment. All subjects who complete T0 outcome measures will be considered “valid”. Based on published data (Fig. 7; (81)), subjects who complete at least 8 weeks (10 mg bid) will be considered “complete”, and included in the primary Aim 2 analyses. Data from all “valid” subjects will be used in separate analyses to understand how MEM EAIP sensitivity impacts the likelihood to “complete” the MEM trial, vs. remain at doses < 10 mg bid, discontinue MEM or add an AChE-I. MEM costs are budgeted through week 24 for all subjects.

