1. Recruitment: One concern is the possible difficulty recruiting sufficient numbers of individuals with mild-to-moderate severity AD. A strength of this application is its intimate ties to active AD clinics and ongoing studies with large samples of well-characterized older adults, many of who have been diagnosed with AD, through collaborations with the UCSD Memory Clinic and Geriatric Medicine Outpatient Clinic, the UCSD ADRC and its affiliated networks throughout San Diego. Recruitment needs for this application are ≈ 2 new subjects / mo. (see "Timeline" and Table 2), with a projected 10% attrition at screening, and 5% attrition at each of the subsequent points of study contact (EAIP testing, weeks 8, 16 and 24), based on past experience and ongoing studies. The target population (mild-to-moderate AD) is not a focus of most ongoing UCSD studies, which prioritize MCI and Pre-MCI subjects; thus, availability of AD patients for this application will support much higher recruitment needs if attrition exceeds projected rates.

2. EAIP measures in AD patients: Our published reports of MEM effects on EAIP measures involved HS and SZ patients, ages 18-55 (65,99). The present application proposes such measures in patients with mild-to-moderate severity AD, ages 50-70 y; thus, both diagnosis and age of the proposed cohort differ from our past experience, and may present unexpected challenges. Importantly, our laboratory group has published extensively on EAIP measures across the full lifespan (eg. ages 18-88: (16)), and in populations with severe dementia and behavioral disturbances (eg. Huntington's Disease (104)), and recently completed a study of EAIP measures in 20 patients with mild-to-moderate severity AD ([name], PI). Thus, neither the clinical symptoms nor age of the proposed cohort should limit the acquisition or interpretation of EAIP measures.

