2. Frequency of monitoring, including any plans for interim analysis and stopping rules (if applicable).

Aim 1: Monitoring can theoretically occur at different frequencies, based on circumstances. Vital signs and visual analog scales (VAS) data of subjects' subjective states are assessed approximately hourly throughout the test day. In the event that the covering MD is contacted by the study technician and deems it necessary, the subject will be examined immediately. A protocol is established for contacting the study pharmacy and unblinding the MD to the study drug if viewed as necessary by the study MD. In the absence of an AE, the results of each test are monitored by the PI within one week of testing, during weekly laboratory meetings. More generally, as described in the "Research Strategy", interim analyses of study results are planned as described below.

Aim 2: Subjects will be treated by their primary physician, who will make all medication adjustments according to the clinical needs of the patient. Patients will be contacted weekly by the Study Coordinator to confirm and record medication adherence. Scheduled monitoring for primary outcome measures will be conducted by the Study Coordinator / RA at 8, 16 and 24 weeks; at that time, the Study Coordinator will also record any changes in MEM dose or addition of other medications, and the reasons for such changes.

3. The process by which Adverse Events (AEs), including Serious Adverse Events (SAEs) will be managed and reported as required:

Aim 1: In the acute presentation, any AE or SAE is managed first by the study technician, per our existing IRB-approved protocol. The on-site study MD is contacted immediately, and personally assesses the subject to determine the appropriate management; because the laboratory is located at the UCSD Medical Center, approximately 50 yards from the UCSD Medical Center Emergency Room, subjects can be escorted to this facility for evaluation and management in the event of a more serious AE.

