Aim 2 involves treatment of all subjects with MEM monotherapy, in a manner (titration rate, final dose) that is common practice in clinical settings. This medication regimen has had longstanding FDA approval for use in moderate-to-severe AD; its use in mild-to-moderate severity AD as proposed here is both common community practice, and has been the focus on many large, multi-site studies (eg. 3,14,40-1,79,81,86). **There is no placebo control group or blinding during this phase, and no restrictions on medication adjustments based on clinical need, and thus none of the procedures are viewed to carry any added experimental risk beyond that encountered in standard community clinical practice.** Events that would preclude a participant from continuing with the intervention are based entirely on the clinical judgment of the patient's physician in consultation with the patient. There are no constraints on this process imposed by the study design. Subjects who finish baseline (T0) and biomarker (Aim 1) testing will be considered “valid”, and subjects who finish 8 weeks of MEM treatment and week 8 outcome measures will be considered “complete”.

Informed Consent Process: Informed Consent is conducted according to standard ADRC protocol, supervised by [name]. The consent process informs a subject about the study, indicates the participation is voluntary and he/she has the right to stop at any time. Risks are enumerated in the informed consent form and described orally during the consent process. The PI has successfully conducted Informed Consent with study subjects for over 25 consecutive years of NIH-funded studies.

INTERIM ANALYSIS

Interim analyses after 6 subjects will assess visual analog scales for subjective drug effects during Aim 1 and potentially adjust MEM test dose as described in the Research Strategy should unanticipated effects (e.g. sedation) be evident. Interim analyses of Aim 1 biomarker data at \approx 6 months (expected n=18) will confirm the fidelity of all EAIP measures, and at \approx 36 months (expected n=54) will guide a future NIA application. **Because the critical test of H2 does not involve an absolute magnitude of clinical change in the subject group, or even a statistically significant group change, there are no plans to stop the study based on an interim analysis demonstrating either outcome.**

DATA AND SAFETY MONITORING

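### The secondary analysis of whether EAIP sensitivity predicts staying on memantine sets an 8-week 'complete' category against open-ended discontinuation and add-on categories, so a patient can fall in both and stops in weeks 8-24 can be missed.

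*Combined protocol and SAP*

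**What the plan says.** The relevant text is in the Research Strategy of the combined protocol and SAP, under the question on incomplete or discontinued subjects. It first raises the possibility that the biomarker "will predict the likelihood to *discontinue* MEM treatment". It then gives the definition: "subjects who complete at least 8 weeks (10 mg bid) will be considered “complete”, and included in the primary Aim 2 analyses". Next it describes a separate analysis, in all 'valid' subjects, of how EAIP MEM sensitivity bears on whether they 'complete' "the MEM trial, vs. remain at doses < 10 mg bid, discontinue MEM or add an AChE-I". In that last sentence the word 'complete' is again marked as a defined term.

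Other places bear on the same categories:

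- *Protection Against Study Risks* restates the rule without a dose: "subjects who finish 8 weeks of MEM treatment and week 8 outcome measures will be considered “complete". It requires biomarker testing for a subject to be 'valid', whereas the Research Strategy requires only the T0 outcome measures.
- *Analytic strategy* adds that the 8 weeks must be monotherapy. It allows dose adjustments in weeks 3-8 and labels patients who cannot tolerate 10 mg bid by the end of week 7 as incomplete treatment.
- *Why MEM monotherapy?* accepts that an AChE-I may be added at any point in the study.
- *Frequency of monitoring*, Aim 2, says: "Patients will be contacted weekly by the Study Coordinator to confirm and record medication adherence". Changes in MEM dose and added medications, with reasons, are recorded at the week 8, 16 and 24 assessments.

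**The concern.** The retention analysis answers the plan's own worry that the biomarker might be related to discontinuation. It needs an outcome that two analysts would code in the same way and that covers the period in which patients can stop.

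As written it has neither. One side of the comparison closes at week 8 and the other stays open to week 24. If 'complete' is applied as defined, every stop after week 8 is recorded as a success. A link between low EAIP sensitivity and later stopping would then be diluted or lost. The later period matters because the plan also wants to learn, in secondary analyses to week 24, whether the benefit lasts longer in MEM-sensitive patients.

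**Working it through.** **1. Classify patients by the stated definitions.**

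| Course | 'Complete' (Research Strategy)? | Opposing category? |
|---|---|---|
| Stops MEM at week 5 | No | Discontinued |
| At 10 mg bid to week 24, no AChE-I | Yes | None |
| At 10 mg bid to week 8, stops MEM at week 12 | Yes | Discontinued |
| At 10 mg bid to week 8, adds AChE-I at week 20 | Yes | Added AChE-I |
| At 10 mg bid to week 8, contact lost at week 14, no event recorded | Yes | None |
| Stays below 10 mg bid, has week 8 measures | No, but yes under *Protection Against Study Risks*, which states no dose | Below 10 mg bid |

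Rows 3 and 4 are in two categories, and row 6 depends on which section is used. Row 5 can only be 'complete'. Nothing in the documents gives a precedence rule, a time window or a time-to-event method for this analysis.

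**2. Reproduce the projected flow (Table 2, month 57).** Inputs are 114 screened, 10% attrition at screening, then "5% attrition at each of the subsequent points of study contact" (*Potential Limitations*, Recruitment).

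- EAIP tested: 114 × 0.90 = 102.6 (Table 2: 103)
- Week 8: 102.6 × 0.95 = 97.5 (98)
- Week 16: 97.5 × 0.95 = 92.6 (93)
- Week 24: 92.6 × 0.95 = 88.0 (88)

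Table 2 reproduces to within rounding.

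**3. Illustrate the period left out.** These are losses of study contact, not MEM stops.

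- EAIP testing to week 8: 103 − 98 = 5
- Week 8 to week 24: 98 − 88 = 10
- Share after week 8: 10 / 15 = 67% (65% before rounding)

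**4. Vary the assumption.** With equal loss d per step, the share after week 8 is [(1 − d) − (1 − d)³] / [1 − (1 − d)³]. This gives 66% at d = 2%, 65% at 5%, 63% at 10% and 61% at 15%. The Recruitment text also lists 5% attrition at EAIP testing, which Table 2 does not apply. Applying it ends the chain at 83.6 instead of 88 and leaves the share at 65%. The share is stable because two of the three follow-up intervals lie after week 8.

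**5. Check what dates will exist.** Weekly contacts should place a MEM stop to about a week. AChE-I additions and dose changes are recorded at three visits, and no dates are promised, so they may be known only to an 8-week interval.

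**The case against.** The strongest reply is that the plan does not ignore these patients. *Analytic strategy* promises separate analyses of those who discontinue or add an AChE-I, and *Why MEM monotherapy?* gives AChE-I adders their own grouping. Both provisions, however, concern clinical outcome in testing H2. Neither says how a stop after week 8 is coded in the retention analysis.

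Three stronger readings are tempting, and the documents do not support them.

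- *A reader might infer that the analysis will have only about five events and so almost no power.* Table 2 counts lost contact. Patients who stay on a lower dose, stop MEM or add an AChE-I can remain under assessment, so they may sit inside the retained 98, 93 and 88. No rate is given for any of the opposing categories. Nor would the 15 projected losses be events under the fix, because a patient lost without a recorded event is censored.
- *A reader might infer that late stops are certain to be counted as successes.* That follows from the literal definition. If discontinuation took precedence, recorded late stops would be captured. The plan does not say which applies.
- *A reader might infer that the H2 test is undermined.* Entry to the primary Aim 2 set depends on the first 8 weeks, so comparing week-8 completers with non-completers does address that selection. Patients lost later stay in the set, and the general statistical approach uses all available data under a missing-at-random assumption.

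It is also fair to say that Cox regression counting any dose reduction as a failure would be a poor replacement, because dose adjustments are permitted in weeks 3-8.

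**Conclusion.** The point holds as a defect in a secondary analysis. The categories overlap, no rule resolves the overlap, and on the literal definition discontinuation or AChE-I addition in weeks 8-24 is labelled 'complete'. This rests on the text alone.

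Its size cannot be computed, because the documents project no rate of MEM discontinuation or AChE-I addition. The 67% of projected contact losses that fall after week 8 indicates scale only if stops are spread over follow-up roughly as contact losses are, which is an assumption. The primary H2 analysis and its sample size are unaffected. The outcome should be settled before the data are analysed, since the coding choice could change what this analysis shows.

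**What to change.** Keep the 8-week rule for entry to the primary Aim 2 set. For the retention analysis:

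1. Include all patients with T0 measures and EAIP data.
2. Use time to first MEM discontinuation or AChE-I addition through Intervention Week 24, modelled on the continuous MEM effect.
3. State one time origin, for example the first MEM dose. On the planned titration (5 mg/d, then 5 mg weekly steps) the target of 20 mg/d is reached after (20 − 5) / 5 = 3 weeks, so Intervention Week 24 ends about 3 + 24 = 27 weeks after the first dose. Fix a horizon on that clock for patients who never reach 10 mg bid, since Intervention Week 1 never starts for them.
4. Treat dates known only to a visit interval as interval-censored, or use a discrete-time model.
5. Censor patients lost without a recorded event, and report such losses by biomarker level.
6. Report never reaching, or not staying at, 10 mg bid as a separate category, consistent with the dose adjustments the plan permits.
7. Tabulate every event type by biomarker group.

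The two sections should also be reconciled on 'valid' and 'complete', including whether dose and monotherapy form part of the definition, and the week 7 limit tied to the same clock.

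The cost is SAP wording and slightly more analysis. The data come from contacts and visits already planned. The downside is that some event times, mainly AChE-I starts, may be coarse.
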